7.1.4 Additional Care of Subjects after the Study

No aftercare is planned for this study.

7.2 Study Evaluations and Procedures

7.2.1 Demographic and Other Baseline Characteristics

7.2.2 Safety

The name and address of each third-party vendor (eg, clinical laboratory) used in this study will be maintained in the investigator's and sponsor's files.

Actual safety assessment times will be monitored and recorded. The sponsor's expectation is that the investigator will ensure that every effort is made to perform all assessments at the precise protocol-scheduled time. Any safety assessment that deviates from the scheduled assessment time set forth in the protocol by more than ± 15 minutes will be considered a protocol deviation.

Ophthalmic assessments are considered safety assessments. If an ophthalmic assessment deviates from the scheduled assessment time set forth in the protocol by more than ± 15 minutes (or 5 minutes for the 15-minute and 30-minute time points), it will be considered a protocol deviation.

All AEs, prior medication use, and concomitant medication use will be assessed and monitored from the time the subject signs the ICF to completion of the study (including to time of screen failure or drop out/discontinuation); see Sections [7.2.2.4](#) and [8.1](#) for further details. The AEs will include nontreatment-emergent AEs (ie, those occurring from the time of informed consent

signature to the first dose of investigational product) and treatment-emergent AEs (ie, AEs occurring after the first dose). While housed at the site, subject safety will also be closely monitored through study procedures and physician oversight.

7.2.2.1 Medical and Medication History

A complete medical and medication history, as well as demographic information, will be collected at the screening visit by a qualified licensed physician, physician's assistant, or a nurse practitioner. The medical history will be reviewed and recorded, including:

- Date of birth
- Sex
- Race and ethnicity
- Recent ingestion of medication (Section 5.1)
- History of respiratory, cardiovascular, renal, gastrointestinal, hepatic, endocrine, hematological, neurological, psychiatric, and other diseases

7.2.2.2 Physical Examination (Including Height and Weight)

A complete physical examination will be performed at the visits specified in [Table 1](#) by a qualified licensed physician, physician's assistant, or nurse practitioner.

The physical examination will include a review of the following body systems:

- General appearance
- Skin
- Head, eyes, ears, nose, and throat
- Spine/neck/thyroid
- Musculoskeletal
- Respiratory
- Cardiovascular
- Neurological
- Abdomen (including liver and kidneys)

Abnormalities identified at the screening visit will be documented in the subject's source documents and on the medical history eCRF page. Clinically significant changes after the screening visit will be captured as AEs on the AE eCRF page, as deemed by the investigator.

Height and weight will be recorded at screening only.

7.2.2.3 Ophthalmologic Examination

Ophthalmologic examinations of both eyes will be performed at the visits specified in [Table 1](#); the time points during each visit are specified in [Table 2](#), [Table 3](#), [Table 4](#), and [Table 5](#) for Cohorts A, B, C, and D, respectively. Both eyes will be assessed at each examination unless otherwise specified.

Manifest Refraction

Manifest refraction will be determined at the following visits in order to assess BCVA:

- Screening
- SDTP (Cohort A only): Day -2
- MDTP (all cohorts): Day -2 and Day 29

The manifest refraction will be repeated if the BCVA has decreased by 10 or more letters. Full instructions for performing the manifest refraction are included in the ophthalmology procedures manual.

Best-Corrected Visual Acuity

Using the manifest refraction, the BCVA will be assessed at distance before slit lamp examination at the following visits:

- Screening
- Midwashout assessment
- SDTP (Cohort A only): Days -2 and -1 and Days 1 and 2
- MDTP (all cohorts): Days -2 and -1 and Days 1, 2, 7, 14, 21, 27, 28, and 29

See [Table 2](#), [Table 3](#), [Table 4](#), and [Table 5](#) for detailed timings by cohort.

Full instructions for measuring BCVA are provided in the ophthalmology procedures manual.

A decrease in BCVA by 6 or more letters may be considered clinically significant (CS) or not clinically significant (NCS) and requires a dilated posterior segment examination. A 10-letter loss in BCVA is considered CS and requires a repeat manifest refraction and dilated posterior segment examination. Clinically significant changes should be recorded as AEs in the source document and eCRF.

Slit Lamp Biomicroscopy

Slit lamp biomicroscopy will be performed at the following visits:

- Screening
- Midwashout assessment

- SDTP (Cohort A only): Days -2 and -1 and Days 1 and 2
- MDTP (all cohorts): Days -2 and -1 and Days 1, 2, 7, 14, 21, 27, 28, and 29

See [Table 2](#), [Table 3](#), [Table 4](#), and [Table 5](#) for detailed timings by cohort.

The anterior segment will be examined through the slit lamp before performing IOP measurements, pachymetry, or graded assessments. The following structures will be evaluated as normal or abnormal. If abnormal, the findings should be described and recorded as either CS or NCS. Any CS findings should be recorded as AEs; the investigator may use his/her discretion to determine whether a finding considered NCS is reported as an AE. Findings and assessment of clinical significance should be recorded in the source documents and eCRF.

The following will be examined at each visit:

- Lids/lashes/lacrimal
- Conjunctiva
- Cornea
- Anterior chamber
- Iris
- Lens

Anterior Segment Graded Assessments

Anterior segment graded assessments will be performed at the following visits:

- Screening
- Midwashout assessment
- SDTP (Cohort A only): Days -2 and -1 and Days 1 and 2
- MDTP (all cohorts): Days -2 and -1 and Days 1, 2, 7, 14, 21, 27, 28, and 29

See [Table 2](#), [Table 3](#), [Table 4](#), and [Table 5](#) for detailed timings by cohort.

Anterior segment graded assessments should be performed during the slit lamp examination but before IOP measurement. The following assessments will be performed:

- Conjunctival redness score assessment
- Corneal haze assessment
- Corneal epithelial integrity assessment by fluorescein staining
- Anterior chamber cell and flare
- Lens opacification (performed during dilated examination only)

The procedures are outlined in [Appendix 2](#); full instructions are provided in the ophthalmology procedures manual.

Any abnormal findings should be described and recorded as either CS or NCS. Any CS findings should be recorded as AEs; the investigator may use his/her discretion to determine whether a finding considered NCS is reported as an AE. Findings and assessment of clinical significance should be recorded in the source document and eCRF.

Intraocular Pressure

Intraocular pressure will be measured at the following visits:

- Screening
- Midwashout assessment
- SDTP (Cohort A only): Days -2 and -1, Days 1 and 2
- MDTP (all cohorts): Days -2 and -1 and Days 1, 2, 7, 14, 21, 27, 28, and 29

See [Table 2](#), [Table 3](#), [Table 4](#), and [Table 5](#) for detailed timings by cohort.

Predose morning IOP assessments must be completed at least 30 minutes before dosing to allow the anesthetic to wear off.

Intraocular pressure will be measured at the slit lamp using Goldmann applanation tonometry. The procedure for measuring IOP is outlined in the ophthalmology procedures manual. Special care must be taken to avoid placing pressure on the globe with the fingers when moving the eyelids to fully expose the cornea.

Intraocular pressure must be measured after assessing the corneal epithelium for fluorescein staining and before pachymetry, gonioscopy, or dilation for posterior segment examination (if being performed).

Two consecutive IOP measurements, to the nearest mmHg, will be made in the designated study eye (designated study eye criteria are detailed in Section [3.1.1](#)); if the 2 measurements differ by more than 2 mmHg, then a third measurement will be performed. All (2 or 3) readings will be used to determine the mean IOP at the given time point. The procedure will be repeated in the nonstudy eye. All measurements will be recorded in the source document and eCRF.

Every effort should be made to obtain an accurate IOP measurement. If the mires are irregular and/or an IOP reading is not obtainable, this should be noted in the source document and eCRF.

Posterior Segment Examination

The posterior segment will be visualized by a fundus examination at the following visits:

- Screening – dilated
- SDTP– nondilated Day -2

- MDTP– nondilated Day -2
- Day 29 – dilated

A dilated posterior segment examination of both eyes should also be performed if the BCVA in either eye decreases by 6 or more letters.

The following structures will be assessed (suggested technique):

- Vitreous (binocular indirect examination)
- Optic nerve head (slit lamp biomicroscopy)
- Cup-to-disc ratio (slit lamp biomicroscopy)
- Macula (slit lamp biomicroscopy)
- Retina vasculature
- Retina, outside of arcades, including periphery
- Choroid

Observations will be described and/or will be graded as normal or abnormal. Abnormal findings will be described. Clinically significant abnormalities will be recorded as AEs; NCS findings will be recorded as AEs at the investigator's discretion. Further details will be specified in the ophthalmology procedures manual.

Gonioscopy

Gonioscopy to assess the iridocorneal angles will be performed at screening and on Day 29. Gonioscopy should be performed after the corneal epithelium has been evaluated for defects with fluorescein and after IOP has been measured but before dilated posterior segment examination (Day 29). The angle of each eye should be graded in all 4 quadrants using the Shaffer grading system.

Noncontact Specular Microscopy

Noncontact specular microscopy will be performed to assess endothelial cell count at the following visits:

- Screening
- SDTP (Cohort A only): Day -1 and Day 2
- MDTP (all cohorts): Day -1 and Days 14 and 29

Details of the procedure will be found in the ophthalmology procedures manual.

Corneal Pachymetry

Corneal pachymetry to assess central corneal thickness will be performed after the predose examination and at 1, 2, 4, and 12 hours after dosing. With the pachymeter set to perform a single measurement, take and record 3 consecutive measurements at each applicable time point at the following visits:

- Screening
- SDTP (Cohort A only): Day -1 and Days 1 and 2
- MDTP (all cohorts): Day -1 and Days 1, 2, 7, 14, and 29

If the range of the measurements is 15 microns or less, the set of readings is acceptable; if not, discard all measurements and repeat until an acceptable set of 3 measurements is obtained. Record all 3 measures in the source document and the eCRF.

See [Table 2](#), [Table 3](#), [Table 4](#), and [Table 5](#) for detailed timings by cohort.

Full details of the procedure are provided in the ophthalmology procedures manual.

Drop Comfort Assessment

Drop comfort assessment should be performed immediately after instillation of investigational product and before IOP assessment (which requires topical anesthetic).

Drop comfort assessments will be performed for the first dose of the day as follows:

- SDTP (Cohort A only): Day 1
- MDTP (all cohorts): Days 1, 7, 14, 21, 27, and 28

Drop comfort assessment will not be captured in the subject's daily journal.

The drop comfort assessment will be performed for each eye except for Cohort A during the SDTP, when only the study eye will be assessed. The assessment will be performed immediately and 1, 2, and 3 minutes after instillation of the investigational product. The subject will be asked to rate drop comfort on a scale of 0-10, where 0=very comfortable and 10=very uncomfortable.

If the score is not ≤ 3 at minute 3, the drop comfort assessment should be repeated at 5, 10, and 15 minutes after dosing until the score is ≤ 3 . If the score is >3 at 15 minutes after dosing, it should be recorded as an AE.

7.2.2.4 Adverse Event Collection

At each study visit, subjects will be questioned in a general way to ascertain if AEs have occurred since the previous visit (eg, "Have you had any health problems since your last visit?"). Adverse events are collected from the time informed consent is signed until Day 88/FU (refer to [Section 8](#)). Adverse events that occur after Day 33 to Day 88/FU should be captured on the AE eCRF page.

7.2.2.5 Vital Signs

Blood Pressure and Pulse Rate

Blood pressure and pulse rate will be measured at the visits specified in [Table 1](#); the time points during each visit are specified in [Table 2](#), [Table 3](#), [Table 4](#), and [Table 5](#) for Cohorts A, B, C, and D, respectively. Additional blood pressure and pulse rate measurements may be performed, as determined by the investigator, in order to ensure appropriate monitoring of subject safety and accurate recording of vital sign measurements. Any changes from baseline that are deemed clinically significant by the investigator are to be recorded as an AE.

The same method for obtaining blood pressure measurement (auscultatory or oscillometric) should be used throughout the study for all subjects (and documented). In addition, the conditions of vital sign measurements should be controlled and as consistent as possible during the study, in order to minimize external variability of the readings. It is advised that measurements be collected at a comfortable room temperature with little to no background noise, using the same (appropriately sized) cuff placed at the same location of the same arm during the study. The bladder deflation rate should be deflated (calibrated for oscillometric method or manually by auscultatory method) at a rate of 2-3 mmHg/s (and the first and last audible sounds recorded as systolic and diastolic pressure) after at least 5 minutes of rest in the assumed position.

The cuff should have a bladder length that is 80% and a width that is at least 40% of arm circumference (a length-to-width ratio of 2:1).

[figure not shown]
The subject should be asked to remove all clothing that covers the location of cuff placement. The subject should be instructed to relax as much as possible for at least 5 minutes before collection. The subject should remain quiet during this time and through the measurement.

The subject should be comfortably seated, with the legs uncrossed, with feet flat on the floor, and the back and arm supported, such that the middle of the cuff on the upper arm is at the level of the right atrium (the midpoint of the sternum).

At the screening visit, blood pressure should be compared between both arms. When there is a consistent interarm difference confirmed over 3 consecutive measurements (>10 mmHg), the arm with the higher blood pressure should be used for inclusion at screening and the last measurement recorded in the eCRF. The same (right or left) arm with the higher blood pressure will be used throughout the study.

For details on blood pressure and pulse procedures, see [Figure 1](#).

Figure 1 Procedures for Screening Vital Signs (Blood Pressure – Pulse)

DBP=diastolic blood pressure; eCRF=electronic case report form; SBP=systolic blood pressure

One reading (seated systolic blood pressure/diastolic blood pressure and pulse rate) should be taken.

The use of automated devices for measuring pulse rate is acceptable, although, when done manually, pulse rate will be measured in the brachial/radial artery for at least 30 seconds. When the timing of these measurements coincides with a blood collection, blood pressure and pulse rate should be obtained before the nominal time of the blood collection.

Body Temperature

Body temperature will be measured at the visits specified in [Table 1](#); the time points during each visit are specified in [Table 2](#), [Table 3](#), [Table 4](#), and [Table 5](#) for Cohorts A, B, C, and D, respectively.

Oral temperature should be taken by placing a digital thermometer under the tongue for at least 30 seconds. Tympanic temperature may also be used.

7.2.2.6 Clinical Laboratory Evaluations

All clinical laboratory assays will be performed according to the laboratory's normal procedures. Reference ranges are to be supplied by the laboratory and will be used to assess the clinical laboratory data for clinical significance and out-of-range pathological changes. The investigator should assess out-of-range clinical laboratory values for clinical significance, indicating if the value(s) is/are not clinically significant or clinically significant. Abnormal clinical laboratory values, which are unexpected or not explained by the subject's clinical condition, may, at the discretion of the investigator or sponsor, be repeated as soon as possible until confirmed, explained, or resolved. Any laboratory results that are determined to be clinically significant or indicative of an AE, as determined by the investigator, will be captured in the clinical database.

The following clinical laboratory assessments will be performed:

Biochemistry

Blood samples (8.5 mL) for serum biochemistry will be collected into a gel separator tube at the visits specified in [Table 1](#). The following parameters will be assessed:

Sodium	Total CO ₂ (Bicarbonate)
Potassium	Albumin
Glucose	Aspartate aminotransferase
Blood urea nitrogen	Alanine aminotransferase
Creatinine	Gamma-glutamyltransferase
Calcium	Alkaline phosphatase
Chloride	Total bilirubin

Phosphorus Uric acid

Total protein β -hCG^a

^a Females only. Only females of child-bearing potential ie, not postmenopausal or surgically sterile, as defined in Section 4.4.1, will be required to have β -hCG evaluated. Reported values of β -hCG that are >1.0 and <6.0 mIU/mL are less than the upper range for non-pregnant, post-menopausal female (7.0-8.3 mIU/mL) and are considered negative.

Hematology

Blood samples (4 mL) for hematology will be collected into an ethylenediaminetetraacetic acid tube at the visits specified in Table 1. The following parameters will be assessed:

Hemoglobin	Total neutrophils (absolute)
Hematocrit	Eosinophils (absolute)
Red blood cells	Monocytes (absolute)
Platelet count	Basophils (absolute)
White blood cell count (total and differential)	Lymphocytes (absolute)

Urinalysis

A urine sample for urinalysis will be collected at the visits specified in Table 1. The following parameters will be assessed:

pH	Blood	Nitrites
Glucose	Ketones	Leukocyte esterase
Protein	Bilirubin	Specific gravity

Microscopic examination will be conducted if protein and/or blood is/are detected during urinalysis. At a minimum, the microscopic examination will consist of red blood cells, white blood cells, casts, and bacteria.

7.2.2.7 Pregnancy Test

For all female subjects (regardless of reproductive potential status), a serum pregnancy test will be performed at the visits specified in Table 1; or if pregnancy is suspected; or on withdrawal of the subject from the study. Pregnancy test results must be confirmed as negative before proceeding in the study.

7.2.2.8 Drug and Alcohol Screen

A urine screen for drugs of abuse and a urine screen or breathalyzer test for alcohol will be performed at the visits specified in Table 1. Additional drug and alcohol screens may be performed at the investigator's discretion.

Urine samples are to be tested for amphetamines, barbiturates, benzodiazepines, cannabinoids, cocaine, methadone, opiate metabolite, and phencyclidine. Additional drugs of abuse, eg, methamphetamines and tricyclic anti-depressants, which are included in currently marketed products for drugs of abuse screening, will also be tested in these samples.

Results of drug and alcohol screens will be reviewed and verified by the study monitor but will not be collected in the eCRF database.

Any positive result for drugs of abuse or alcohol at screening or on Day -1 will exclude the subject from further participation in the study.

7.2.2.9 Serology Screen

At the screening visit, a blood sample of approximately 8 mL will be collected into a serum separator tube to test for the presence of HIV, HBsAg, and HCV antibody.

The test results must be confirmed negative before randomization. If a test result is positive, the subject will be excluded from entering the study. Results of the virology screen will be reviewed and verified by the study monitor but will not be collected in the eCRF database.

7.2.2.10 Antidrug Antibody Testing

A blood sample of approximately 6 mL will be collected to test for antidrug antibodies in serum at the visits specified in [Table 1](#). On dosing days, samples will be collected before the first dose of the day. A full description of the ADA sample collection, handling, storage, and shipping is provided in the laboratory manual.

Any subject with newly developed antidrug antibodies at the Day 60 (Day 88/FU) assessment, which is 60 days after dosing, may require follow-up. This will be discussed as necessary by the principal ophthalmologist and medical monitor on a case-by-case basis.

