Vital signs ^l	X	X	X	X	X	X		X	X	X	X		X		X		X		X	X	X	X		
Biochemistry, hematology, and urinalysis	X		X			X		X		X			X		X		X		X	X		X		
Electrocardiogram	X		X	X	X	X		X	X	X	X		X		X		X		X	X		X		
PK blood sampling					X					X										X				
Antidrug Ab blood sampling								X						X							X			X
Drop comfort assessment ^m					X				X			X		X		X			X	X				

Table 1 Overall Schedule of Events

Study Visit	Screening and WO 1 ^{a,t}		SDTP Baseline ^b		SDTP (Cohort A) ^b		WO 2 ^c	MDTP Baseline ^d		MDTP ^d (Cohorts A, B, C, and D)											29/ ET ^{f,t}	FU Call ^g	88/ FU ^s , v			
	-28	-14/ MWOA ⁱ	-2	-1	1	2		-2	-1	1	2	3-6	7	8-13	14	15-20	21	22-25	26	27	28 ^e					
Study Day Window (Days)	-14	±2			0	0				0	0		±2		±2		±2					0	±2	±4		
IP Administration (Per Cohort for Each Dose Level)^q																										
Cohort A					X					X	X	X	X	X	X	X	X	X	X	X	X	X				
Cohort B										X	X	X	X	X	X	X	X	X	X	X	X	X				
Cohort C										X	X	X	X	X	X	X	X	X	X	X	X	X				
Cohort D										X	X	X	X	X	X	X	X	X	X	X	X	X				

Ab=antibody; BCVA=best-corrected visual acuity; ET=early termination; HBsAg=hepatitis B surface antigen; HCV=hepatitis C virus; HIV=human immunodeficiency virus; IOP=intraocular pressure; IP=investigational product; MDTP=multiple-dose treatment period; MWOA=midwashout ophthalmic assessment; PK=pharmacokinetic; SDTP=single-dose treatment period; WO=washout.

- ^a Subjects in all cohorts are to be washed out of current medications for up to 28 days, as specified in Section 5.2.2. The washout may start from Day -28 onwards, depending on the length of washout required. A MWOA will be performed on both eyes either 14±2 days after a subject starts the washout period or 14±2 days after a previous MWOA. Subjects will continue not to take prohibited medications until discharge from the site on Day 29 of the MDTP.
- ^b The SDTP will occur in Cohort A only. Subjects in Cohort A will be admitted to the unit on Day -3 (optional early check-in to unit if more convenient for the subject) or Day -2 before the morning assessments and will be discharged on Day 2 after completion of the evening assessments. All subjects must have checked in to the unit before the ophthalmologic assessments on Day -2.
- ^c For Cohort A only, there will be a washout period of 3-14 days between the SDTP and the MDTP.

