^q SDTP dosing (Cohort A only): investigational product (SHP639 ophthalmic solution or placebo) will be administered once on the morning of Day 1. MDTP dosing: Cohort A=once daily, Cohort B=twice daily, Cohort C=3 times daily, Cohort D=4 times daily; the final dose will be administered on the morning of Day 28. Dose administration will occur during waking hours.

^r Lens opacification is graded at screening and Day 29, during the scheduled dilated exam. The lens assessment that is part of the slit lamp exam on those days should not report graded opacification findings, but should report other lens-related findings that are visible during the non-dilated exam.

^s The Day 88 visit is 60 days post last dose (Day 28 of MDTP).

^t For Screening, MWOA, and Day 29 visits only one round of ophthalmic assessments needs to be done in the morning.

^u At check-in for overnight stays the following assessments will be performed: physical exam, drugs of abuse screening, alcohol breathalyzer, vital signs, hematology, chemistry, urinalysis, and a single ECG.

^v The Day 88/FU visit is labeled “Day 88” based on a subject’s duration of participation from Day 1 (1st dose) of the MDTP. Subjects in cohort A1, A2, and A3 will have been in the study for a longer duration due to the SDTP.

^w At screening IOP may be done at any time during the day. At MWOA (D-14), IOP should be done at 10:00am +3 hours. IOP only needs to be done at one time during screening, MWOA, and Day 29.

Refer to Section 7.1 for guidance on the priority order of assessments. Refer to [Table 2](#) (Cohort A), [Table 3](#) (Cohort B), [Table 4](#) (Cohort C), and [Table 5](#) (Cohort D), for details of time points within each visit.

Table 2 Detailed Schedule of Events – Cohort A

Assessment	Days Performed (Screening through D29) ^f	Predose/ Morning ^a										
			0 m	30 m	1 h	2 h	3 h	4 h	6 h	8 h	12 h	
Assessment Window (minutes)			0	±5	±15	±15	±15	±15	±15	±15	±15	±15
Alcohol breath test	SCR, D-14, SDTP: D-2, MDTP: D-2 and D-1, D1, D14, D21, D26.	X										
Serum pregnancy test (female subjects)	SCR, SDTP: D-2, MDTP: D-2, D1, D26, D29	X										
Biochemistry, hematology, and urinalysis	SCR, SDTP: D-2, D2. MDTP: D-2, D1, D7, D14, D21, D26, D27, D29.	X										

Ab=antibody; BCVA=best-corrected visual acuity; D=day; ECG=electrocardiogram; FU=follow up; h=hours; IOP=intraocular pressure; m=minutes; MDTP=multiple-dose treatment period; PK=pharmacokinetic; SCR=screening; SDTP=single-dose treatment period.

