
IOP assessments on Screening and MWOA (D-14) need to be done one time during the day only.
 
At screening: IOP may be measured at any time during the day.
 
At MWOA (D-14) IOP will be measured in the morning at 10:00am (+3 hours).
 
Additional assessments other than the “morning assessments” at screening and MWOA (D-14) do not need to be conducted.
	
Table 1, Table 2, Table 3, Table 4, Table 5

Clarification of last study drug dose:
 
Subjects will be administered the last dose of study drug on the morning of Day 28. Add a footnote to tables 2, 3, 4, and 5.
	
Table 2, Table 3, Table 4, Table 5

Clarification of Corneal Pachymetry Timing: The timing of IOP and Corneal Pachymetry will be more closely aligned to allow for procedure scheduling at sites: Corneal Pachymetry will be performed at the following time points for all applicable visit days: Predose/Morning, 1 hour post dose, 2 hours post dose, 4 hours post dose, and 12 hours post dose.
	
Table 2, Table 3, Table 4, Table 5 Section 7.2.2.3

Clarification of Baseline: The Baseline “BL” Column will be removed from Tables 2, 3, 4, and 5. All reference to “BL” will be removed from the column titles “Days Performed” and all reference to visits will be done by day number. Removed all reference to “Baseline” in Section 7.2.2.3
	
Table 2, Table 3, Table 4, Table 5 Section 7.2.2.3

Clarification of Antidrug antibody (Ab) sampling in Table 1: remove “X” from Day 26 as no sample will be collected at Day 26. Clarification of Antidrug Ab sampling in Tables 2, 3, 4, 5. The column titled “Days Performed” incorrectly identifies Antidrug Ab blood sampling to be collected at the screening visit. No ADA samples will be taken at screening. Clarification of Antidrug Ab sampling at Day 26: No ADA samples will be taken at Day 26. In Table 2 only: Antidrug Ab blood sampling time point was added to Table 2 at the predose/morning time point. Site personnel should collect the Antidrug Ab blood sample at the predose/morning time point.
	
Table 1, Table 2, Table 3, Table 4, Table 5

The volume of blood to be drawn per subject has changed due to the removal of an ADA sample at the Screening visit for all subjects.
	
Table 11 and Table 12 Section 7.2.5

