^m Drop comfort assessments will be performed immediately and 1, 2, and 3 minutes after instillation of the investigational product; to be assessed at morning doses only. If the score is not ≤ 3 at minute 3, the drop comfort assessment should be repeated at minutes 5, 10, and 15 until the score is ≤ 3 . If the score is >3 at minute 15, it should be recorded as an adverse event.

ⁿ If BCVA decreases by 6 or more letters, then a dilated posterior segment examination should be performed.

^o Manifest refraction should be repeated if the BCVA in either eye decreases by 10 or more letters.

^p Conjunctival redness will be evaluated using the Efron scale.

^q SDTP dosing (Cohort A only): investigational product (SHP639 ophthalmic solution or placebo) will be administered once on the morning of Day 1. MDTP dosing: Cohort A=once daily, Cohort B=twice daily, Cohort C=3 times daily, Cohort D=4 times daily; the final dose will be administered on the morning of Day 28. Dose administration will occur during waking hours.

^r The Day 88 visit is 60 days post last dose (Day 28 of MDTP).

^s For Screening, MWOA, and Day 29 visits only one round of ophthalmic assessments needs to be done in the morning.

^t At check-in for overnight stays the following assessments will be performed: physical exam, drugs of abuse screening, alcohol breathalyzer, vital signs, hematology, chemistry, urinalysis, and a single ECG.

^u The Day 88/FU visit is labeled "Day 88" based on a subject's duration of participation from Day 1 (1st dose) of the MDTP. Subjects in cohort A1, A2, and A3 will have been in the study for a longer duration due to the SDTP.

^v At screening IOP may be done at any time during the day. At MWOA (D-14), IOP should be done at 10:00am +3 hours. IOP only needs to be done at one time during screening, MWOA, and Day 29.

Table 2 Detailed Schedule of Events – Cohort A

Assessment	Days Performed (Screening-D29) ^f	Predose/ Morning ^a	0 m	30 m	1 h	2 h	3 h	4 h	6 h	8 h	12 h
		Gonioscopy ^c	SCR, D29.	X							
Specular microscopy, noncontact	SCR. SDTP: D-1, D2. MDTP: D-1, D14, D29.	X									
Corneal pachymetry	SCR. SDTP: D-1, D1, D2. MDTP: D-1, D1, D2, D7, D14, D29.	X			X	X		X			X
Antidrug Ab blood sampling	D-2, D14, D29, D88/FU	X									
Drugs of abuse	SCR, D-14, SDTP: D-2, MDTP: D-2 and D-1, D1, D14, D21, D26.	X									
Alcohol breath test	SCR (D-42), SCR (D-14). SDTP: BL (D-2), MDTP: BL (D-2 and D-1), D1, D14, D21, D26.	X									

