11.5 Antidrug Antibody Testing

A blood sample of approximately 6 mL will be collected to test for antidrug antibodies (ADA) in serum at the visits specified in Table 1. On dosing days, samples will be collected before the first dose of the day. Any subject with newly developed antidrug antibodies at the Day 60 assessment may require follow-up. Results of ADA testing will be listed by individual subject. The summarization format will be based on the data result type.

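### Cohorts A1-A3 have no antidrug-antibody sample before first exposure, so an active subject positive at MDTP Day -2 cannot be classed as pre-existing or induced

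*Protocol*

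**What the plan says.** - Protocol 7.2.2.10 states that blood "will be collected to test for antidrug antibodies in serum at the visits specified in" Table 1. It then gives the follow-up rule: "Any subject with newly developed antidrug antibodies at the Day 60 (Day 88/FU) assessment, which is 60 days after dosing, may require follow-up". SAP 11.5 repeats it in shorter form: "Any subject with newly developed antidrug antibodies at the Day 60 assessment may require follow-up".
- Table 1 in both documents marks the ADA row at MDTP Day -2, Day 14, Day 29 and Day 88. Screening and all SDTP columns are blank.
- SAP Table 2, the detailed Cohort A schedule, gives the ADA days as "D-2, D14, D29, D88/FU" without saying which period the Day -2 entry belongs to. Other Cohort A rows do name the period. The pregnancy-test row in protocol Table 2 reads "SCR, SDTP: D-2, MDTP: D-2, D1, D26, D29".
- Cohort A receives one drop in one eye on SDTP Day 1 and then enters the MDTP after a gap: "For Cohort A only, there will be a washout period of 3-14 days between the SDTP and the MDTP" (protocol Table 1, footnote c).
- SAP 11.5 plans a by-subject listing and leaves the summary format open. It defines neither an ADA baseline nor what counts as newly developed.

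**The concern.** ADA is one of the safety assessments named in protocol 9.9.1, and safety is the primary objective. To call an antibody new, one needs a sample from before the drug was given. In Cohorts B-D, Day -2 is such a sample. In Cohort A the visit with the same name comes after the SDTP dose. A positive result there in an active subject could be antibody the subject already had or a response to that dose, and no earlier sample exists to decide between them.

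For laboratory tests, vital signs and ECG, the SAP defines separate pre-dose baselines for the SDTP and the MDTP (SAP 11.2 to 11.4). For ADA it defines none. If Day -2 were used as baseline in every cohort, an antibody induced by the single dose would look pre-existing in Cohort A, and the same label would mean different things in A and in B-D.

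**Working it through.** **Where the first sample falls.** Protocol 7.2.2.10 defers to Table 1. The row "Antidrug Ab blood sampling" has its first mark in the MDTP Day -2 column. The biochemistry row fixes the column position: it is marked at both SDTP Day -2 and MDTP Day -2, whereas the ADA row has only the second mark. The Amendment 1 entry in the protocol history agrees that there is no earlier draw: "No ADA samples will be taken at screening".

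**How many samples there are.** Protocol Tables 11 and 12 reproduce:
- Cohort A: 72 + 8 + 93.5 + 44 + 24 = 241.5 mL.
- Cohorts B-D: 48 + 8 + 76.5 + 36 + 24 = 192.5 mL.
- Difference: 49 mL = PK 24 + biochemistry 17 + hematology 8 + ADA 0.

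ADA is 4 × 6 = 24 mL in both tables, so the SDTP adds no ADA draw. This rules out a fifth sample. It does not show in which period the Day -2 sample is taken; Table 1 alone shows that.

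**Days from the SDTP dose to MDTP Day -2.** The dose is on SDTP Day 1, so SDTP Day 2 is one day later. With a washout of w = 3 to 14 days:
- MDTP Day -2 falls w days after SDTP Day 2: w + 1 = 4 to 15 days.
- w full days lie between SDTP Day 2 and MDTP Day -2: w + 2 = 5 to 16 days.
- w runs from SDTP Day 2 to MDTP Day 1, with Day -2 two days before Day 1: w + 1 − 2 = 2 to 13 days.

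On every reading the sample follows first exposure, by 2 to 16 days overall.

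**How many subjects lack a pre-exposure sample.** 3 cohorts × 5 active = 15. Twelve cohorts less D1, which was dropped, leaves 11 × 5 = 55 active, and 15/55 = 27%. SAP section 13 reports a repeat of Cohort B3. If that repeat also had 5 active subjects (an assumption), the share is 15/60 = 25%. The 3 × 2 = 6 placebo subjects in A1-A3 had no drug in the SDTP and are not affected.

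**What can still be classified among active Cohort A subjects.**

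| MDTP Day -2 | Day 14, 29 or 88 | Reading |
|---|---|---|
| Negative | Positive | Newly positive; identifiable |
| Negative | Negative | No antibody detected |
| Positive | Any | Pre-existing or induced by the single dose; not separable |

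Only the last row is lost. In Cohorts B-D a Day -2 positive precedes any dose, so the same row can be read as pre-existing.

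**The case against.** A reader might infer that new antibodies cannot be identified at all in the once-daily cohorts. The documents do not support that: a change from negative at MDTP Day -2 to positive later is visible with the samples already scheduled. Nor are 15 subjects misclassified. Fifteen lack the sample; the number left indeterminate is unknown and could be zero.

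Four further objections deserve a reply.

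- **The Day -2 entry in SAP Table 2 may mean SDTP Day -2.** That would be a pre-exposure sample. The entry is ambiguous, but this reading contradicts Table 1, to which 7.2.2.10 defers. Either way the two tables must be made to agree.
- **Misclassification is hypothetical.** This stands in part. Neither document states a baseline rule that would class an induced antibody as pre-existing, and follow-up is discretionary, case by case. The visible defect is an undefined term together with a missing sample. A definition alone would serve Cohorts B-D; it would not supply Cohort A's missing sample.
- **The exposure is small.** One drop in one eye, with very low or undetectable systemic exposure in animals, may produce few positives. That limits the importance of the point without closing the gap.
- **The schedule change is too late, and separation is already planned.** The SAP is dated 30 August 2018, after an interim analysis planned for November 2017 that was to unmask Cohorts A and B, so Cohort A dosing is probably over. Protocol 9.9.2 already lists and summarizes ADA by dose and cohort. This stands for the schedule in subjects already dosed. The SAP still needs a sentence saying what the Cohort A Day -2 sample is and how a positive is to be classed.

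**Conclusion.** The point holds in a limited form. Under Table 1 of both documents, none of the roughly 15 active subjects in A1-A3 has an ADA sample before first exposure. The consequence is confined to those positive at MDTP Day -2, in whom pre-existing antibody cannot be told from a response to the single dose. Cohorts B-D and the Cohort A placebo subjects are unaffected.

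This rests on reading Table 1 as the governing schedule and on 5 active subjects per cohort as planned; replacements would change the count slightly. It is a modest defect in a named safety assessment, worth correcting because the correction costs very little.

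**What to change.** **Cohort A subjects not yet dosed, or any repeat of Cohort A** (protocol 9.6 allows any cohort to be repeated): take the baseline ADA sample at SDTP Day -2, when blood is already drawn for biochemistry and hematology. There are two ways to do this:
- Move the existing tube. The total stays at 4 samples and 241.5 mL, but there is no ADA reading between the two periods.
- Add a tube and keep MDTP Day -2. ADA becomes 5 × 6 = 30 mL and the Cohort A total 241.5 + 6 = 247.5 mL; update Table 11.

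In both cases, name the period of the Day -2 draw in Tables 1 and 2 of both documents so that they agree.

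**Cohort A subjects already dosed:** add to SAP 11.5 that
- MDTP Day -2 is a post-single-dose sample in Cohort A and a pre-exposure sample in Cohorts B-D;
- active Cohort A subjects positive at that visit are indeterminate, not pre-existing;
- a subject negative there and positive later counts as newly positive;
- treatment-emergent ADA in Cohort A is presented separately from Cohorts B-D.

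The cost is a schedule-table edit, at most one 6 mL tube per subject at an existing draw, and a few lines in the SAP. For subjects already dosed the SAP text makes the reporting accurate but cannot recover the missing sample.
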